4.3. Justification for Dose

In this study 5 dose regimens of TBA-7371 will be tested over a 14-day treatment period: 100 mg QD, 100 mg BID, 200 mg QD, 100 mg TID and 400 mg QD.

From a safety perspective the dose selection is justified by the fact that in study TBA7371-001 single doses of 100, 200, 400 and 800 mg and multiple doses over 14 days of 100, 200 and 400 mg QD were tested: doses from 100 to 400 mg/day are considered suitable for further development assuming proper mitigation steps are in place (see Section 2.3). See Investigator Brochure for more detail.

From an activity perspective, no human data are available. PK-PD modelling of animal data, taken together with human PK data in healthy volunteers, suggest that 200 mg QD or above may be necessary to achieve a meaningful bactericidal effect.

Whereas QD dosing is an important feature of the target product profile for TBA-7371, the introduction in the study design of a twice daily (100 mg BID) and a three times daily (100 mg TID) regimen will allow assessment of the impact of daily dose fractionation vs. QD dose on the bactericidal activity and the safety/tolerability profile of TBA-7371. This information will be valuable for further development of this and other investigational drugs with similar mechanism of action.

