4.2. Scientific Rationale for Study Design

The dose escalation approach, with go/no-go decision on each escalation step to be taken by the IDMC based on the complete safety dataset from lower dose cohort(s), has been chosen to maximize the safety of participants, against the background of the safety and tolerability profile observed in study TBA-7371-001. As mentioned above, the two most frequent treatment emergent adverse events, namely heart rate increase and eye symptoms, had a dose-dependent (above 100 mg QD) frequency and were mostly mild and transient.

The level of masking, in this study, which includes all personnel involved in CFU counts for the primary endpoint (see Section 6.3.2), ensures balance of methodological excellence and feasibility, and is considered adequate for the stage of development of TBA-7371.

Whereas the 3 dose escalation steps will be conducted in an open-label manner, within the 2nd escalation, participants will be randomized to Cohort II or Cohort III. This approach is justified because Cohorts II and III have the same total daily dose of TBA-7371 (200 mg) and strengthens the design of the study.

Within each cohort, participants will be randomized to TBA-7371 or HRZE control with a 5:1 ratio (15 TBA-7371 vs. 3 HRZE). This unequal randomization is justified by the fact that HRZE data from all cohorts will be pooled; hence, if all 5 cohorts will be allowed to enter the trial, the target size of the control group (N=15) will be the same as the TBA-7371 groups.

The target population is adult males and females with untreated, rifampicin-sensitive, uncomplicated pulmonary TB. This population is ideal for the assessment of the bactericidal activity of a new drug.

In this trial, QD, BID and TID schedules will be tested. The scientific rationale is that some symptoms appear to be associated with C_{max}. It is therefore possible that fractionation of the daily dose could improve the tolerability profile and the benefit-risk ratio.

Primary endpoints are: 1) EBA of TBA-7371 as determined by the slope of log CFU count on solid media culture from screening through Day 14; and 2) frequency of participants with serious and/or severe (\geq Grade 3) AEs throughout the treatment. The value of EBA to predict clinical efficacy is outlined in Section 2.2.2. Combined SAEs and severe AEs are considered the best indicators of the overall burden and acceptability of the treatment to patients.

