6.3. Measures to Minimize Bias: Randomization and Masking

6.3.1. Randomization

Participants will be enrolled in one of 5 cohorts in 3 sequential escalation steps as follows.

- Cohort I: TBA-7371 100 mg QD or HRZE (Rifafour® e-275) QD for 14 days.
- First escalation step (from Cohort I to Cohorts II and III). Participants will be randomized to Cohort II OR Cohort III.
 - Cohort II: TBA-7371 100 mg BID or HRZE (Rifafour® e-275) QD for 14 days.
 - Cohort III: TBA-7371 200 mg QD or HRZE (Rifafour® e-275) QD for 14 days.
- Second escalation step (from Cohort II and Cohort III to Cohort IV)
 - Cohort IV: TBA-7371 100 mg TID or HRZE (Rifafour® e-275) QD for 14 days.
- Third escalation step (from Cohort IV to Cohort V)
 - Cohort V: TBA-7371 400 mg 400 QD or HRZE (Rifafour® e-275) QD for 14 days.

Across Cohorts I, IV, and V, the design is non-randomized and open label, whereas the design is randomized with respect to Cohort II and III, which have the same total daily dose (200 mg). Within each cohort the design is randomized, active-controlled and open label. Within each cohort participants will be randomized unequally in a 5:1 ratio to TBA-7371 (N=15) or HRZE (N=3).

Participants will be randomized on Day -1 or Day 1 based on a randomly-generated sequence of participant identification (identifier) numbers (randomization schedule) using a validated Interactive Voice/Web Response System (IVRS/IWRS). Before the study is initiated, the telephone number and call-in directions for the IVRS and/or the log in information and instructions for the IWRS will be provided to the study sites.

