9.2. Sample Size Determination

Approximately 90 participants will be randomized 5:1 to either intervention arm, totaling $N = 15$ for each TBA-7371 treatment and control groups.

Bactericidal effect

Based on Diacon et al. (2013)³, standard deviations associated with $BA_{CFU}(0-14)$ were relatively consistent across 5 treatment groups, ranging from 0.05 to 0.08. If we assume conservatively that the true SD of the $BA_{CFU}(0-14)$ measures for the TBA-7371 treatment groups is equal to 0.1, then with $N=15$ per group we have 80% (90%) power to detect a true group mean $BA_{CFU}(0-14)$ reduction of 0.067 (0.079), using a 1-sided alpha = 5%. For reference, the observed $BA_{CFU}(0-14)$ reduction in Diacon et al, 2013³ were 0.040, 0.056, 0.077, 0.104, and 0.112 for Bedaquiline 100 mg, 200 mg, 300 mg, 400 mg and standard HRZE, respectively.

Safety

With $N=15$ per group, we have approximately 80% (90%) probability to observe at least one AE if the true AE rate is 10% (15%). We have only 54% probability to observe at least one AE if the true AE rate is 5%. Across the five TBA-7371 treatment groups ($N=75$), we have 90% probability to observe at least one AE if the true AE rate is 3.0%.

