6.2 Sample Size Determination

Anticipating all cohorts are to be assessed in the study, approximately 90 participants will be randomized in a 5:1 ratio to either TBA-7371 or control group, totaling N = 15 participants for each TBA-7371 treatment and control groups (receiving treatment with HRZE).

Bactericidal effect

Based on Diacon et al. (Diacon, 2013) standard deviations associated with BAcfu(0-14) were relatively consistent across 5 treatment groups, ranging from 0.05 to 0.08. If we assume conservatively that the true standard deviation of the BAcfu(0-14) measures for the TBA-7371 treatment groups is equal to 0.1, then with N = 15 per group we have 80% (90%) power to detect a true group mean BAcfu(0-14) reduction of 0.067 (0.079), using a 1-sided alpha = 5%. For reference, the observed BAcfu(0-14) reduction in Diacon et al, 2013 were 0.040, 0.056, 0.077, 0.104, and 0.122 for Bedaquiline 100 mg, 200 mg, 300 mg, 400 mg and standard HRZE, respectively.

Safety

With N = 15 per group, we have approximately 80% (90%) probability to observe at least one AE if the true AE rate is 10% (15%). We have only 54% probability to observe at least one AE if the true AE rate is 5%. Across the five TBA-7371 treatment groups (N=75), we have 90% probability to observe at least one AE if the true AE rate is 3.0%.

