regression model for individual participants in each treatment group in order to ensure the Akaike information criteria (AIC) values for the linear and bilinear models are based on the same form of the likelihood function. Suggested starting values for the parameters are $(\alpha, \beta_1) = (6, 0)$ however a grid search approach can be followed to obtain sensible starting values.

If the linear regression model is selected, the average change in $\log_{10}\text{CFU}/\text{mL}$ count per day over 14 days will be estimated by the constant linear regression slope estimate, $\hat{\beta}_{1i}$, i.e.

$$BA_{CFU}(0 - 14)_i = \hat{\beta}_{1i}.$$

Therefore, for each participant, slopes will be estimated using both bilinear and simple linear regression models, and the better fit model based on lower AIC will be selected for that participant and used to estimate $BA_{CFU}(0-14)$. The $\log_{10}\text{CFU}/\text{mL}$ screening measurement used in the model will be the average of the two individual screening measurements. $BA_{CFU}(0-14)$ will be calculated for each participant within a treatment group individually, and then used as the response variable in an ANCOVA model, with a fixed effect for treatment group and screening $\log_{10}\text{CFU}/\text{mL}$ count as a covariate. Treatment group means from the ANCOVA model will be used to quantify the evidence that each of the treatment group mean $BA_{CFU}(0-14)$ is less than 0 (i.e., that the treatment group mean has a negative slope on average). The mITT population will be used for the primary efficacy analysis with analyses using the per-protocol population performed to assess the robustness of results. The SAS PROC MIXED procedure will be used to fit an ANCOVA model.

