  class <treatment group>(ref=HRZE);
  model <Avg. Slope(0-14)> = <treatment group> + <screening
logCFU> /
* LSmeans used to obtain 90 CIs;
  lsmeans <treatment group> / cl alpha=0.1;
* 6 LSMestimate statements used to obtain 1-sided p-values -
NOTE: HRZE will refer to #6 below if used as reference, the #1-5 will
be as indicated in model;;
  lsmestimate <trt> 'trt #1' 1 0 0 0 0 0 / lower alpha = 0.05;
  lsmestimate <trt> 'trt #2' 0 1 0 0 0 0 / lower alpha = 0.05;
  lsmestimate <trt> 'trt #3' 0 0 1 0 0 0 / lower alpha = 0.05;
  lsmestimate <trt> 'trt #4' 0 0 0 1 0 0 / lower alpha = 0.05;
  lsmestimate <trt> 'trt #5' 0 0 0 0 1 0 / lower alpha = 0.05;
  lsmestimate <trt> 'trt #6' 0 0 0 0 0 1 / lower alpha = 0.05;
run;
```

SAS code for random intercepts and slopes model (day = relative to baseline study day, trt = treatment group with HRZE as reference):

```
proc mixed data=<dataset>;
  class <treatment group>(ref=HRZE) <subject>;
  model logCFU = <day> + <trt> + <day*trt> + <screening logCFU>;
  random int day / subject=<subject> type=un;
* The first 6 estimate statements used to obtain correct 1-sided p-
values - NOTE: HRZE will refer to #6 below if used as reference, the
#1-5 will be as indicated in model;
  estimate "Avg slope Tr 1" day 1 trt*day 1 0 0 0 0 0 / cl lower
alpha =0.05;
  estimate "Avg slope Tr 2" day 1 trt*day 0 1 0 0 0 0 / cl lower alpha
=0.05;
  estimate "Avg slope Tr 3" day 1 trt*day 0 0 1 0 0 0 / cl lower alpha
=0.05;
  estimate "Avg slope Tr 4" day 1 trt*day 0 0 0 1 0 0 / cl lower alpha
=0.05;
  estimate "Avg slope Tr 5" day 1 trt*day 0 0 0 0 1 0 / cl lower alpha
=0.05;
  estimate "Avg slope Tr 6" day 1 trt*day 0 0 0 0 0 1 / cl lower alpha
=0.05;
* The next 6 estimate statements used to obtain correct 90% CIs;
  estimate "Avg slope Tr 1" day 1 trt*day 1 0 0 0 0 0 / cl alpha =0.1;
  estimate "Avg slope Tr 2" day 1 trt*day 0 1 0 0 0 0 / cl alpha =0.1;
  estimate "Avg slope Tr 3" day 1 trt*day 0 0 1 0 0 0 / cl alpha =0.1;
  estimate "Avg slope Tr 4" day 1 trt*day 0 0 0 1 0 0 / cl alpha =0.1;
  estimate "Avg slope Tr 5" day 1 trt*day 0 0 0 0 1 0 / cl alpha =0.1;
  estimate "Avg slope Tr 6" day 1 trt*day 0 0 0 0 0 1 / cl alpha =0.1;
run;
```

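### The trial randomises 100 mg BID against 200 mg QD at the same daily dose, but no planned analysis estimates the difference between them

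*Protocol*

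**What the plan says.** **The aim.** Protocol 4.3 says that the BID and TID regimens "will allow assessment of the impact of daily dose fractionation vs. QD dose on the bactericidal activity and the safety/tolerability profile of TBA-7371". Protocol 2.3 and 4.2 give the reason: some symptoms seem to follow Cmax, so dividing the daily dose might improve tolerability.

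**The design.** Protocol 6.3.1 separates Cohorts II and III from the other, sequentially enrolled cohorts: "the design is randomized with respect to Cohort II and III, which have the same total daily dose (200 mg"). Protocol 4.2 adds, in a sentence cut here before its last word: "This approach is justified because Cohorts II and III have the same total daily dose of TBA-7371 (200 mg) and strengthens the design of the".

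**The efficacy analysis.** SAP 11.1.1: "Treatment group means from the ANCOVA model will be used to quantify the evidence that each of the treatment group mean" slope is below zero. The ANCOVA code in SAP Appendix 4 has "6 LSMestimate statements used to obtain 1-sided p-values", each with a single coefficient of 1 and the rest 0. Cohorts II and III form testing Group 2, where each is tested against zero. The secondary CFU, TTP and LAM analyses (SAP 11.1.2 and 11.2) also set each group against zero. The mixed model in SAP 11.1.3.2 reports one slope per group.

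**The safety analysis.** SAP section 12 summarises by treatment group. Protocol 9.4.2.1 mentions only a comparison with control, and declines to make it formally because the samples are small.

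**The concern.** The protocol states a question about fractionation and randomises two arms so that it can be answered fairly, but the plan stops before the estimate that would answer it. The other divided-dose regimen cannot fill the gap: 100 mg TID and 400 mg QD differ in daily dose (300 against 400 mg) and are enrolled one after the other without randomisation between them.

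With no pre-specified difference, a reader of the report has two substitutes. One is to see which regimen was declared a success. The other is to compare two separate intervals by eye. Neither gives an interval for the difference. Success status has a further problem: Group 2 is formally tested only if both Group 1 regimens pass, so it may have no formal result at all.

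**Working it through.** **Inputs.** SAP 6.2 gives the group size: "totaling N = 15 participants for each TBA-7371 treatment and control groups". Protocol 9.2 assumes that the SD of the BA_CFU(0-14) "measures for the TBA-7371 treatment groups is equal to 0.1", and cites SDs of 0.05 to 0.08 from an earlier bedaquiline study. Alpha is 5% one-sided. The six-group ANCOVA with one covariate has 90 − 6 − 1 = 83 error df.

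**1. The plan's own figure.** One-sample t-test, 14 df, one-sided 5%, non-centrality = effect × √15 / SD.
- 0.067 × 3.873 / 0.1 = 2.59, power 79.4% (stated 80%).
- 0.079 × 3.873 / 0.1 = 3.06, power 89.7% (stated 90%).

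The figures reproduce as a test of one arm against zero. A two-arm comparison with 15 per arm and 28 df would have 43% two-sided power for a difference of 0.067. The trial was not sized for comparisons between arms.

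**2. How often pass/fail separates equal arms.** A split means that the larger p is ≥ 0.05 and the smaller is < 0.025. For two nearly independent arms its probability is about 2 × P(p < 0.025) × P(p ≥ 0.05). At SD 0.1 and 0.067, with 83 df: 2 × 0.728 × 0.177 = 0.26. A simulation of 400,000 pairs with a shared pooled SD gives 0.254.

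These rates hold once Group 2 is reached. If Group 1 has the same true effect, one-arm power with 83 df is about 69%, 82.4% and 91.8% at the three effects. Both Group 1 arms then pass in about 0.48, 0.68 and 0.84 of trials (the squares).

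| True reduction, both arms (SD 0.1) | Split, once Group 2 is reached | Split per trial, Group 1 effect equal |
|---|---|---|
| 0.056 | 35% | 17% |
| 0.067 | 25% | 17% |
| 0.079 | 14% | 12% |

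At 0.067, once Group 2 is reached, the split rate falls to 10% at SD 0.08 and to nearly 0% at SD 0.05.

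**3. What a direct contrast would give.** 90% CI half-width = t(0.95, 83 df) × SD × √(2/15) = 1.663 × SD × 0.365.
- SD 0.05: 0.030
- SD 0.08: 0.049
- SD 0.10: 0.061

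For scale, the bedaquiline 100 mg and 400 mg reductions quoted in Protocol 9.2 differ by 0.104 − 0.040 = 0.064.

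**4. Binary safety endpoints.** Wald 95% half-width, 15 against 15, for assumed equal rates: 1.96 × √(2 × 0.2 × 0.8 / 15) = 0.29 at 20%, and 1.96 × √(2 × 0.5 × 0.5 / 15) = 0.36 at 50%.

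**The case against.** The strongest reply is that fractionation is a rationale in Protocol 4.3 and not an objective, endpoint or hypothesis. On that view a Phase 2a trial sized per arm against zero may reasonably describe the two regimens side by side. Much of this stands. At the planning SD the 90% half-width of 0.061 is 91% of the 0.067 effect used for power, so the contrast would bound only large differences. The safety differences would be wider still, in line with the small-sample caution in Protocol 9.4.2.1. It does not justify leaving out the estimate: the interval for a difference costs nothing and is more informative than two separate intervals.

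A reader might infer more than the documents support:
- **That the randomised comparison is wasted.** The two arms appear together in by-group tables and in least-squares means with 90% CIs. Exposure-response analyses (SAP 13.2 and 13.3) bear on fractionation indirectly, and Protocol 4.2 says exposure-response will guide regimen selection. What is missing is the between-arm estimate. TBA-7371 against HRZE is also randomised within each cohort.
- **That safety data are only listed.** SAP 12.1.1 and 12.2 give proportions with 95% CIs, and SAP 12.5 gives summaries, threshold proportions and plots.
- **That equal regimens will usually be split by the rule.** The 35%, 25% and 14% apply at SD 0.1, which the protocol calls conservative, and only once Group 2 is reached.
- **That the trial should be enlarged.** Nothing in the plan promises a powered comparison of regimens.

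**Conclusion.** The gap is real and worth closing, though modest. The plan states a fractionation question and randomises for it at equal daily dose, but specifies no estimate of the BID-QD difference in efficacy or safety. Success status against zero would be a poor substitute under the protocol's conservative SD and a smaller hazard at the cited SDs. The split rates assume equal true effects in the two arms, 15 analysed per arm, and step-down testing read as standard Hochberg within each group. The per-trial rates also assume the same true effect in Group 1. Exploratory analysis plans are separate and were not available; the exploratory objectives listed in Protocol 3.3 and SAP 5.3 do not name this comparison.

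**What to change.** In Protocol 9.4.1 and SAP 11.1.1, pre-specify one supportive estimate, outside the alpha hierarchy and labelled as not powered: the difference in BA_CFU(0-14), 100 mg BID minus 200 mg QD, with a two-sided 90% CI from the existing ANCOVA.

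Identify the arms by named treatment level, or confirm the class-level order before writing coefficients. SAP Appendix 4 leaves the numbering open. With the order listed in SAP 9.1 the row is 0 1 −1 0 0 0. If text labels sort alphabetically with HRZE last, that same row contrasts 100 mg QD with 100 mg TID.

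Optionally, add to SAP section 12 the BID-minus-QD risk differences with 95% CIs for any new eye symptom and for a heart-rate rise of 25% or more on Days 1 to 15. Label them descriptive and imprecise (about ±29 to ±36 points).

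State that fractionation will be interpreted from these estimates and not from which regimen passed the test against zero.

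The cost is a few lines of text and one code statement, with no added patients, data or alpha.

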4.4. End of Study Definition

A participant is considered to have completed the study if he/she completes the final visit on Day 42. The end of the study is defined as the date of the last visit of the last participant in the study or last scheduled procedure shown in the SoA for the last participant in the trial.

5. Study Population

Prospective approvals of protocol deviations to enrollment criteria, also known as protocol waivers or exemptions, are not permitted.

Recruitment

Participants will be recruited from communities with known high burden of TB transmission and disease. Various methods of recruitment may be used, such as community information sessions, advertising, referrals, word-of mouth, or solicitation through participants previously known to the clinical site.

Recruitment materials, if any, will be approved by the appropriate Institutional Review Board/s (IRBs) or Independent Ethics Committee/s (IECs). Interested participants will be invited to participate in the informed consent process.

5.1. Inclusion Criteria

Age

1. 18 to 60 years of age (inclusive) at the time of signing the informed consent.

Weight

2. Body weight within 40 and 100 kg (inclusive).

Disease Characteristics

3. Untreated, rifampicin-sensitive pulmonary TB, as defined by all of the following:
 - a. isoniazid urine screen negativity
 - b. sputum smear positivity for acid-fast bacilli using fluorescent microscopy, defined as at least 1+ on the International Union Against Tuberculosis and Lung Disease (IUATLD)/WHO scale
 - c. chest X-rays which in the opinion of the investigator is consistent with TB
 - d. Mtb positivity on molecular test (GeneXpert®)
 - e. rifampicin sensitivity on molecular test (GeneXpert®).

Sputum Production

4. Participants must be able to produce at least 10 mL of sputum during the screening overnight sputum collection (two attempts can be made during Day -7 to -3 to meet the volume requirement if the patient is domiciled at the site for both), as assessed by a Sponsor-approved central laboratory.

Childbearing potential

5. Female and male participants should be of non-childbearing potential or using an effective method of birth control.

Non-childbearing potential is defined as follows:

- a. participant is not heterosexually active or practices sexual abstinence, OR
- b. female participant or sexual partner has undergone bilateral oophorectomy, bilateral tubal ligation and/or hysterectomy, OR

- c. female participant or sexual partner has been postmenopausal with a history of no menses for at least 12 consecutive months, OR
- d. male participant or sexual partner has undergone vasectomy or bilateral orchidectomy at least three months prior to screening, OR
- e. male participant with pregnant sexual partner (for duration of the study) who does not have any other sexual partners.

An effective method of birth control is defined as follows:

- a. double barrier method, which can include any 2 of the following: a male condom, diaphragm, cervical cap, or female condom (male and female condoms should not be used together), OR
- b. barrier method (one of the above) combined with hormone-based contraceptives or an intra-uterine device for the female participant or partner, AND
- c. participant willing to continue practicing one of the above-mentioned birth control methods throughout 14-day Study Treatment Phase and for 4 weeks after the last dose of study medication or discontinuation from study medication in case of early withdrawal.

See Section 10.3 (Appendix 3) for more information on contraceptive guidance and collection of pregnancy information

Informed Consent

- 6. Participants must be capable of giving signed informed consent as described in Section 10.1 (Appendix 1), which includes agreeing to compliance with the requirements and restrictions listed in the informed consent form (ICF) and in this protocol.

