5.3. Lifestyle Considerations

Avoidance of pregnancy during the study: see Section 5.1.

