10.2.7.4. SAE and Serious ADR Reporting Schemes

10.3. Appendix 3. Contraceptive Guidance and Collection of Pregnancy Information

Definitions:

Female of Childbearing Potential (FOCBP)

A female is considered fertile following menarche. If fertility is uncertain (e.g. amenorrhea in adolescents) and a menstrual cycle cannot be confirmed before first dose of study intervention, additional evaluation should be considered. If in doubt, the participant should be considered fertile.

Women in the following categories are not considered FOCBP

1. Premenarchal
2. Documented hysterectomy, bilateral salpingectomy or bilateral oophorectomy
 - For individuals with permanent infertility due to an alternate medical cause other than the above, (e.g. mullerian agenesis, androgen insensitivity), investigator discretion should be applied to determining study entry.

Note: Documentation can come from the site personnel's: review of the participant's medical records, medical examination, or medical history interview.

Contraception Guidance:

Women physically capable of pregnancy must agree to use an acceptable method of avoiding pregnancy **for 1 month after the last dose of study medication**.

Male participants of childbearing potential must agree to use an acceptable method of contraception for 3 months after the last dose of the study medication and must also refrain from sperm donation through 3 months after receiving the last dose of study medication.

Acceptable methods of avoiding pregnancy include:

- sexual abstinence (not engaging in sexual intercourse)
- a confirmed sterile partner

Or at least 2 of the below contraceptive methods

- hormonal contraceptives (oral, injection, transdermal patch, or implant)
- Intra Uterine Device (IUD)
- male or female condom
- diaphragm

Collection and Reporting Pregnancy Information

Male and female participants will be provided with information on acceptable methods of contraception as part of the informed consent process and will be asked to sign the ICF stating that they understand the requirements for avoidance of pregnancy.

In the event of a pregnancy by a female participant or pregnancy by a sexual partner of a male participant, the processes outlined below must be followed.

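### Inclusion criterion 5(c) gives men 4 weeks of contraception after the last dose; Appendix 3 requires 3 months and no sperm donation

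*Protocol*

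**What the plan says.** Criterion 5 of Protocol Section 5.1 opens by covering both sexes: "Female and male participants should be of non-childbearing potential or using an effective method of birth control". For participants who qualify through birth control, item (c) gives one duration with no split by sex: "throughout 14-day Study Treatment Phase and for 4 weeks after the last dose of study medication", or after discontinuation for those who withdraw early. Sperm donation is not mentioned. The line after criterion 5 points to Appendix 3 "for more information on contraceptive guidance and collection of pregnancy information".

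Appendix 3 (Section 10.3) sets separate rules. Women capable of pregnancy must avoid it "for 1 month after the last dose of study medication". The rule for fertile men is longer; they "must agree to use an acceptable method of contraception for 3 months after the last dose of the study medication". The appendix then adds a second restriction for the same men over the same period, that they do not donate sperm.

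Two other places bear on the point. Section 5.3 says only: "Avoidance of pregnancy during the study: see Section 5.1". Criterion 6 makes inclusion depend on informed consent, which includes "agreeing to compliance with the requirements and restrictions listed in the informed consent form (ICF) and in this protocol".

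**The concern.** The protocol gives two contraception periods for the same men, and the shorter one stands in the eligibility criteria. Section 8.1 bases eligibility for randomization on Sections 5.1 and 5.2 and does not name Appendix 3 there. Section 5.3 sends the reader on pregnancy avoidance to Section 5.1. The pointer to Appendix 3 after criterion 5 reads as a pointer to supplementary detail, with no sign that a period about three times as long applies to men.

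A man willing to use contraception for only 4 weeks satisfies 5(c) as written but not Appendix 3. A site working from the criterion could counsel him to the shorter period and say nothing about sperm donation. At stake is a reproductive-safety condition for an investigational drug.

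Timing adds to the concern. Under Section 4.4 a participant's final visit is Day 42, nominally the day on which the 5(c) period ends. The whole of the extra male period therefore falls after the last scheduled contact, and no later visit is planned at which wrong advice could be corrected.

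**Working it through.** No sample size, power or alpha figure is involved. The check is a comparison of the texts plus calendar arithmetic.

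**Inputs**

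- Last dose: Day 14, for a participant who completes treatment.
- Criterion 5(c): 4 weeks = 28 days after the last dose, both sexes.
- Appendix 3, women: 1 month = 28 to 31 days, depending on the calendar.
- Appendix 3, men: 3 months = 89 to 92 days, depending on which three calendar months apply.

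**End of each period**

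| Source | Calculation | Ends on |
|---|---|---|
| Criterion 5(c), women and men | 14 + 28 | Day 42 |
| Appendix 3, men, shortest | 14 + 89 | Day 103 |
| Appendix 3, men, longest | 14 + 92 | Day 106 |

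**Differences**

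- Men: 89 − 28 = 61 days at least and 92 − 28 = 64 days at most, or about 2 months.
- Women: 28 − 28 = 0 days at least and 31 − 28 = 3 days at most, so there is no material conflict.
- Sperm donation: no restriction in criterion 5, against 3 months in Appendix 3.

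For a man who stops treatment early, both periods start sooner, but the gap between them is still 61 to 64 days.

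**Whether both texts are current.** Both stand in the body of Version 4, so the conflict does not depend on superseded wording. As background only, the document history (Appendix 7) records that the male 3-month text entered Appendix 3 in Version 3, and it lists no matching change to criterion 5. An incomplete amendment is the likely explanation, though the protocol does not say so.

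**The case against.** The strongest reply is that the two rules are cumulative and the longer one already binds. Appendix 3 is mandatory in its wording, and criterion 6 makes agreement to the protocol's requirements part of inclusion. On that reading a man who accepts only 4 weeks fails criterion 6, and one who complies for 3 months satisfies both texts. Appendix 3 also assigns contraception information to the consent process and asks participants to sign that they understand the requirements. The consent form may therefore state 3 months.

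The wording of Section 5.3 is also limited to the study period. That period nominally ends on Day 42, and up to then the two durations do not conflict. Finally, neither document states a male-mediated reproductive risk for TBA-7371, so a length of time has been shown but not a harm.

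Much of this stands as mitigation. The 3-month rule is in the protocol, the reader is not cut off from it, and the exposure is potential. It does not remove the inconsistency. Criterion 6 binds participants to a protocol that contains both periods, and no text says which one prevails. Satisfying both by following the longer period helps only a man who has been told 3 months. The consent step works only if the form draws on one unambiguous source. That the risk is unquantified is a reason for restraint in the rating, but it does not justify leaving an eligibility criterion at odds with the protocol's own safety requirement.

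**Conclusion.** The concern holds. For men who qualify through birth control, criterion 5(c) understates the Appendix 3 contraception period by 61 to 64 days and omits the 3-month restriction on sperm donation. The female periods agree.

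The figure assumes that 4 weeks means 28 days and that 3 months means calendar months. The documents give no expected number of men, so the number affected is not estimated. Whether any man would be misadvised depends on the consent form, which was not available for review. The endpoints, analysis populations and statistical analysis are unaffected. The correction should be made, with the degree of concern kept in proportion to the partial mitigation already in the protocol.

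**What to change.** Amend criterion 5(c) so that the period runs through the Study Treatment Phase and then, from the last dose or discontinuation, for 4 weeks in women and 3 months in men, with no sperm donation by men for those 3 months. Have Section 5.3 cite Appendix 3 as well as Section 5.1. Check that the consent form carries the same periods. If the sponsor did intend 4 weeks for men, it should document that decision and change Appendix 3 instead. Either way, the protocol should state one male period.

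The drafting cost is one line, one cross-reference and one check. As an amendment it needs IRB/IEC approval before implementation (Section 10.1.1), and if the consent form has to change, participants must be re-consented (Section 10.1.5). Both are routine. Visits, sample size and analysis do not change. No recruitment restriction is added, because Appendix 3 already asks men for 3 months.
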